12.1	DECLARATION OF HELSINKI	43
12.2	INSTITUTIONAL REVIEW BOARD	43
12.3	INFORMED CONSENT PROCESS	43
12.4	EXCLUSION OF WOMEN, MINORITIES, AND CHILDREN (SPECIAL POPULATIONS)	44
12.5	SUBJECT CONFIDENTIALITY	45
13	A HANDLING AND RECORDKEEPING	45
13.1	SOURCE DOCUMENTS AND ELECTRONIC CASE REPORT FORMS:	45
13.2	DATA MANAGEMENT RESPONSIBILITIES	45
13.3	DATA CAPTURE METHODS	46
13.4	TYPES OF DATA	46
13.5	TIMING/REPORTS	46
13.6	STUDY RECORDS RETENTION	46
13.7	PROTOCOL DEVIATIONS	47
14	FINANCING AND INSURANCE	47
15	PUBLICATION POLICY	47
16	LITERATURE CITED	48
17	APPENDICES	49
17.1	SUMMARY OF PRECLINICAL ANIMAL STUDIES	49
17.2	TOXICITY TABLES FOR SOLICITED ADVERSE EVENT INTENSITY	50
17.3	TOXICITY GRADING SCALE FOR LABORATORY ADVERSE EVENTS	51
17.5	COMMON TOXICITY CRITERIA FOR GRADING UNSOLICITED ADVERSE EVENTS	52

PROTOCOL SYNOPSIS

Purpose: This study will evaluate the safety and immunogenicity of the experimental malaria vaccine AMA1-C1/Alhydrogel[®], and the ability of the TLR-9 agonist CPG 7909 oligodeoxynucleotide (ODN) to augment antibody responses to the vaccine and alter the Th1/Th2 bias. The vaccine preparations to be studied contain an equal mixture of AMA1 from two different clones of *Plasmodium falciparum* (FVO and 3D7), both produced separately as recombinant proteins expressed by *Pichia pastoris* (PpAMA-1 FVO and PpAMA-1 3D7). Bulk PpAMA-1 antigens were purified from culture medium of transformed yeast grown in a 60L fermenter. The correctly folded PpAMA-1 was purified from this mixture by a combination of affinity, ionic, hydrophobic and gel filtration chromatography. Purified PpAMA-1 FVO and PpAMA-1 3D7 were subsequently mixed and adsorbed onto aluminum hydroxide gel (Alhydrogel[®]). The CPG 7909 ODN formulation used in this study (CPG 7909) is manufactured by Coley Pharmaceutical Group. Subjects will be randomly assigned to receive Alhydrogel[®] formulated vaccine with or without CPG 7909 in a point of use formulation.

Research Environment: The study will be conducted at the University of Rochester Vaccine and Treatment Evaluation Unit (VTEU).

Subjects: Subjects for this study will be healthy adults between the ages of 18 and 45 years with no history of malaria or of recent travel to malaria-endemic areas. Subjects will be enrolled in three consecutive dose-escalation cohorts with review by a Safety Monitoring Committee between cohorts.

Subject Participation: Subjects will receive three vaccinations with the AMA1-C1/Alhydrogel[®] vaccine formulated in Alhydrogel[®] with or without CPG 7909 adjuvant over 2 months (0, 1, 2 months) by intramuscular (IM) injection. Subjects will have multiple blood samples obtained over the next 6 months.

Variables to be Investigated: Samples will be tested for binding antibody to AMA1 and for ability to inhibit the growth of plasmodia in vitro. In addition, antigen-specific activated B cells in peripheral blood will be enumerated, as well as the relative ratio of antigen-specific Th1-like and Th2-like T cells.

Risk/Benefits: The risks of participating in this study are those associated with administration of AMA1-C1/Alhydrogel[®] and of CPG 7909, and include local pain, systemic inflammatory responses including fever and influenza-like symptoms, and induction of autoimmune responses. As with any other investigational vaccine, there are unknown risks. Subjects may derive no benefit from participation in this study. Development of effective vaccines to prevent malaria is an important societal benefit.

Confidentiality: Volunteers will have code numbers and will not be identified by name.

1 BACKGROUND INFORMATION

1.1 MALARIA VACCINES

As reported by the World Health Organization in 2002, the worldwide incidence of malaria is approximately 300 million clinical cases annually, with approximately one million deaths per year attributed to malaria alone or in combination with other diseases¹. Most of the mortality occurs among children under 5 years of age in sub Saharan Africa. Of the four species of malaria that infect humans, *Plasmodium falciparum* is responsible for the majority of these deaths. Mounting drug resistance of the malaria parasite, as well as widespread resistance of mosquitoes to insecticides make these control strategies increasingly unrealistic. A vaccine that would reduce both mortality and morbidity secondary to *P. falciparum* infection would be a valuable resource in the fight against this disease.

Apical membrane antigen-1 (AMA1) is produced by mature *P. falciparum* schizonts in infected erythrocytes², and localizes in the electron-dense neck of the rhoptry, an apical secretory organelle of the merozoite involved in red cell invasion³. The protein is subsequently exported to the merozoite surface at around the time of rupture of the schizont-infected erythrocyte⁴. AMA1 is not carried into the erythrocyte during invasion, but remains associated with the invasion interface and the areas of the merozoite that have not yet entered the erythrocyte^{4,5}. Although its exact function remains undetermined, these observations suggest that it performs a role during merozoite invasion of erythrocytes.

The AMA1-C1/Alhydrogel[®] vaccine has been tested in two human clinical trials under an U.S. F.D.A. Investigational New Drug Application (BB-IND-10944). The first Phase 1 trial in the U.S. demonstrated that the vaccine was well-tolerated. No safety concerns were identified. The immunogenicity data showed modest immune responses could be elicited in humans, and that functional antibody was present using the growth inhibition assay. The second Phase 1 trial started in Mali in May 2004. The adult subjects have received two vaccinations thus far, and a third booster vaccination will be administered 12 months after the first vaccination. No safety concerns related to vaccination in this study have been identified thus far.

Recently, it has been demonstrated that polynucleotides containing a CPG 7909 motif can significantly enhance B cell responses to co-administered antigens via interactions with toll-like receptor 9 (TLR-9). Therefore, this study will evaluate whether the addition of CPG 7909 will improve the antibody response to the AMA1-C1/Alhydrogel[®] vaccine. Additionally, CPG 7909 is known to induce a Th1-biased immune response which has been shown to be more

effective for inducing cell-mediated immune responses. CPG 7909 has been administered to humans on its own as an investigational cancer therapeutic agent and as a vaccine adjuvant with two licensed vaccines to healthy adult subjects without significant safety concerns under U.S. F.D.A. IND (BB-IND-11795).

1.2 PRELIMINARY STUDIES

1.2.1 Preclinical studies with AMA1-C1/Alhydrogel®

A total of 3 individual preclinical trials have been conducted to assess the safety and immunogenicity of the AMA1-C1/Alhydrogel® + CPG 7909 vaccine (see Appendix 17.1 for a tabular summary of the preclinical trials) prior to human clinical trials.

This combination has been tested by IM administration in mice, rats, and guinea pigs. The AMA1-C1/Alhydrogel® + CPG 7909 formulation was more immunogenic in the animals as compared to AMA1-C1/Alhydrogel® given without CPG 7909. No clinically significant adverse effects have been observed.

1.2.2 Clinical trials with AMA1-C1/Alhydrogel®

There have been two human clinical trials to date using the recombinant AMA1-C1/Alhydrogel® vaccine.

The first clinical trial to use AMA1-C1/Alhydrogel® was performed at Johns Hopkins University (Baltimore, MD) and is currently in volunteer follow up stages. The vaccine candidate which was tested at Hopkins is the same product to be used in this protocol without the CPG 7909. Thirty subjects have received up to 3 immunizations (Day 0, 28 and 180) with either 5, 20, or 80 µg doses of AMA1-C1/Alhydrogel® in an open label dose escalating study. No safety concerns were identified. Adverse events related to vaccination have been limited to local injection site reactions, which have been mild to moderate in severity. There was a dose response with the 80 µg group giving the highest antibody levels at day 42 (14 days after the second vaccination) and at day 194 (14 days after the third vaccination).

The second clinical trial using AMA1-C1/Alhydrogel® was started in Mali in May 2004. The study is a randomized double blind controlled trial. Fifty-four healthy Malian adults were randomized 2:1 to receive either AMA1-C1/Alhydrogel® at either 5, 20, or 80 µg doses, or a comparator vaccine. Thus far, each of the 3 dose groups have received two vaccinations. No safety concerns have been identified at this time.

Additionally, a recombinant AMA1 3D7 vaccine using Montanide ISA720 as the adjuvant has been tested in Australia. A Phase 1 study was conducted using the recombinant AMA1

ectodomain expressed in and refolded from *Escherichia coli*. Thirty-five healthy adults received either 5 µg (n=10), 20 µg (n=10), or 80 µg (n=9) of protein emulsified in Montanide ISA 720, or Montanide ISA 720 alone (n=6) as a control. Immunizations were administered as 0.5 mL IM injections; the second dose was given 2-3 months following the first dose, and the third dose was given 6 months following the second. The vaccine was generally well tolerated, although a number of subjects developed local AEs, in both the vaccine and control groups. A total of 32 AEs occurred that were possibly or probably related to the vaccine: one was systemic (headache and flushing after the first vaccination), and the remaining events were local reactions. The local AEs consisted mainly of pain and swelling at the injection site (13 mild, 17 moderate, and 1 severe). The formulation, a water-in-oil emulsion of antigen in Montanide ISA720, is not used in any approved vaccines, and is expected to elicit a significant proportion of local adverse reactions.

1.3 NAME AND DESCRIPTION OF INVESTIGATIONAL PRODUCTS

1.3.1 AMA1-C1/Alhydrogel[®] Malaria Vaccine.

Both recombinant AMA1 FVO and AMA1 3D7 are highly purified 62 kDa proteins that correspond to the ectodomain of *P. falciparum* (FVO) AMA1 and *P. falciparum* (3D7) AMA1, respectively. AMA1 FVO and AMA1 3D7 each consist of the ectodomain of the mature protein found in parasites with the addition of a 6-histidine C-terminal tag to allow purification of the protein. AMA1 FVO and AMA1 3D7 were purified from the fermentation supernatant using a combination of affinity, ionic, hydrophobic, and gel filtration chromatography. The purification process was designed to separate full-length product from degraded material as well as non-product-related contaminants. AMA1 FVO and AMA1 3D7 bulk antigens were both manufactured at the WRAIR Bioproduction Facility (Silver Spring, Maryland) according to cGMP. The bulk antigens were prepared in unbuffered, isotonic saline without preservatives.

1.3.2 Alhydrogel[®]

Aluminum hydroxide gel (HCl Biosector, Denmark) has been extensively used as an adjuvant in many licensed human vaccines. Aluminum-containing adjuvants are in routine human use and contained in many licensed human vaccines. Alhydrogel[®] is supplied sterile, in isotonic saline without preservatives.

1.3.3 CPG 7909 Oligodeoxynucleotide

CPG 7909 (Coley Pharmaceutical Group, Wellesley, MA) is an investigational agent under U.S. F.D.A I.N.D (BB-IND-11795). CPG 7909 is a short synthetic oligodeoxynucleotide of the following sequence: 5'-TCG TCG TTT TGT CGT TTT TTT CGA-3', with all nucleotides linked with phosphorothioate bonds. CPG 7909 (VaxImmune) is manufactured according to cGMP standards and is supplied in sterile vials at 10 mg/mL in phosphate buffered saline for IM administration.

1.4 KNOWN AND POTENTIAL RISKS AND BENEFITS

Possible local vaccine reactions include pain, swelling, erythema, induration, limitation of limb movement for several days, lymphadenopathy, or pruritus at the injection site. Local SC nodules, believed to be granulomatous reactions to aluminum hydroxide, have been observed with use of aluminum hydroxide-based adjuvants. Thus, most aluminum hydroxide-adsorbed vaccines are injected IM rather than SC. Systemic reactions such as fever, chills, headache, fatigue, malaise, myalgia, joint pain, may also possibly occur. Immediate hypersensitivity reactions including urticaria, anaphylaxis, or other IgE mediated responses are possible as with any vaccine.

CPG 7909 is a potent immune activator, and has the potential to overcome the normal tolerance of the immune system for self antigens. In a number of murine models, administration of CPG 7909 has been associated with development of certain autoimmune phenomenon (see Coley Investigator Brochure, Appendix 3). However, the relevance of this finding to humans is unclear because while TLR-9 receptors are widely distributed among immune cells in mice, they appear to be restricted to B cells and plasmacytoid dendritic cells in humans. No subject in any study to date with CPG 7909 oligonucleotides has developed signs or symptoms of autoimmune disease.

In animal studies, CPG 7909 oligodeoxynucleotides (ODN) given by themselves only rarely induce the production of anti-dsDNA antibodies. However, if the CPG 7909 ODN are administered as a complex together with a foreign protein or other antigen that can elicit T cell help, then it is likely that antibodies against the CPG 7909 ODN will be produced, and these

may cross-react with dsDNA. Vaccination of humans with a CPG 7909 ODN together with an antigen capable of binding to the ODN could be expected to result in the production of IgG anti-ODN antibodies, which could cross react with self DNA.

This phenomenon may have been observed in clinical studies with CPG 7909. One normal subject in the Hepatitis B study, and 27/155 subjects in studies involving use of CPG 7909 as an antineoplastic agent, have developed detectable antibody to double-stranded DNA. The specificity of these antibodies for ss or ds DNA has not been determined at this time, and the reactivity of the antibody with the CPG 7909 ODN itself has not been determined. These antibodies have generally declined to baseline after cessation of CPG 7909, and have not been associated with other autoimmune phenomenon, and their possible clinical significance is unknown. Subjects in this study will be closely monitored for laboratory evidence or clinical signs or symptoms of autoimmunity.

As with any investigational vaccine, there is a theoretical possibility of risks about which we have no present knowledge. Subjects will be informed of any such risks should further data become available.

Female participants will be cautioned of the unknown risk of study vaccines to the fetus and will be advised to use adequate birth control methods for the duration of the study.

Risks occasionally associated with venipuncture include pain and bruising at the site of venipuncture, lightheadedness, and syncope (rarely).

Subjects will not receive any direct benefit from participation in this study. It is hoped that information gained in this study will contribute to the development of a safe and effective malaria vaccine.

1.5 DOSAGE AND ROUTE OF ADMINISTRATION

Subjects in this study will be randomized to receive either

Group A: 20 µg AMA1-C1/Alhydrogel[®] with 377 µg Aluminum and 500 µg CPG 7909

Group B: 80 µg AMA1-C1/Alhydrogel[®] with 368 µg Aluminum and 500 µg CPG 7909

Group C: 80 µg AMA1-C1/Alhydrogel[®] with 368 µg Aluminum alone

All groups will receive three injections separated by one month between injections of the same dose level. All doses will be given by IM injection in the deltoid muscle in alternating arms.

1.6 CONDUCT OF THE STUDY

The investigator(s) must adhere to the protocol as detailed in this document. The Principal investigator will be responsible for enrolling only those volunteers who have met protocol eligibility criteria.

A physician may implement a deviation from, or a change in, the protocol to eliminate immediate hazard(s) to trial subjects without prior NIAID and/or IRB/IEC approval. As soon as possible, the implemented deviation or change, the reasons for it and if appropriate, the proposed protocol amendment(s) must be submitted:

- To the IRB/IEC for review and approval/favorable decision
- To NIAID for agreement; and if required
- To the appropriate regulatory authorities.

Any physician-implemented changes as described above and all other protocol violations must be reported to the Data Coordinating Center in a timely manner. Protocol violations that result in an adverse event must be reported on an AE/SAE form and on the Protocol Deviation form and faxed to PPD at [name] within 72 hours of site awareness. The Data Coordinating Center must be notified by submission of the form in the Internet Data Entry System (IDES) within 72 hours for all deviations. The following items must be addressed on the Protocol Violation/Deviation CRF or contained in supplemental documentation attached to the CRF, as appropriate:

- Nature of the error
- Standard reporting information (subject's clinical status before and after the event)
- Steps taken to review the error
- Steps taken to assure the error will not occur again.

Protocol violations must also be reported to the site's IRB in accordance with IRB policies.

1.7 DESCRIPTION OF THE STUDY POPULATION

The study will be conducted in healthy adults ages 18 to 45 with no history of malaria or recent travel to malarious areas.

2 OBJECTIVES

2.1 PRIMARY OBJECTIVES

- 2.1.1 To assess the safety, reactogenicity of the AMA1-C1/Alhydrogel[®] + CPG 7909 vaccine.

2.2 SECONDARY OBJECTIVES

- 2.2.1 To demonstrate that the addition of CPG 7909 improves the immune responses to AMA1-FVO and AMA1-3D7, as compared to AMA1-C1/Alhydrogel[®] at day 70 (14 days after 3rd vaccination).
- 2.2.2 To determine the dose of AMA1-C1/Alhydrogel[®] + CPG 7909 that generates the highest serum antibody levels of AMA1-FVO and AMA1-3D7 at day 70.
- 2.2.3 To assess and compare the duration of antibody responses to AMA1-FVO and AMA1-3D7 proteins by enzyme-linked immunosorbent assay (ELISA) over an 8 month period (6 months after 3rd vaccination).
- 2.2.4 To perform exploratory studies of B and T cell populations both before and after vaccination.

2.3 TERTIARY OBJECTIVES:

The following objectives are for informational purposes only:

- 2.3.1 To measure the biological activity of the antisera by an in vitro parasite growth inhibition assay using FVO and 3D7 parasites.
- 2.3.2 To determine the relationship between anti-AMA1 antibody concentration as determined by ELISA and the degree of in vitro growth inhibition of *P. falciparum*.
- 2.3.3 To determine the relative specificity of the antibodies to a range of AMA1 serotypes in addition to FVO and 3D7, as judged by ELISA and growth inhibition on a select panel of parasites with typed AMA1 antigens.

3 TRIAL DESIGN AND METHODS

3.1 TRIAL ENDPOINTS

The trial endpoints are described below:

3.1.1 Safety

Safety endpoints include the frequency and severity of local and systemic adverse events after each dose reported on the subject diary card (solicited adverse events) or reported by subjects spontaneously (unsolicited adverse events) and the presence of abnormal clinical laboratory tests after immunization in each group.

3.1.2 Immunogenicity

Immunogenicity endpoints include the frequency and titer of vaccine induced neutralizing and binding antibody, and the presence and quantity of antigen-specific B cells and CD4 and CD8 T cells producing specified cytokines following vaccination.

3.2 STUDY DESIGN

The study is a dose escalating Phase 1 clinical trial in healthy adult subjects designed to evaluate the safety, reactogenicity, and immunogenicity of the AMA1-C1 malaria vaccine formulated on Alhydrogel[®] co-administered with CPG 7909. The subjects will be randomized within group to receive one of 2 doses of AMA1-C1/Alhydrogel[®] + CPG 7909 or 80 µg of AMA1-C1/Alhydrogel[®] without CPG 7909. The subjects will be blinded to which vaccine they are receiving, AMA1-C1/Alhydrogel[®] with or without CPG 7909. This study will be staggered such that dose escalation will not occur until the lower dose group has received two vaccinations at days 0 and 28. The safety data up to and including day 35 (7 days post-vaccination #2) will be reviewed prior to dose escalation by the Safety Monitoring Committee.

After providing written informed consent, subjects will undergo eligibility screening, including medical history, physical examination, hematology testing, liver and renal function testing, HIV, Hepatitis B and C screening, rheumatoid factor, anti-dsDNA and ANA testing, and urinalysis; pregnancy testing will be performed on female subjects. For participants who are eligible, the Day 0 visit will be scheduled to receive the first dose of vaccine. Subjects will be observed for immediate reactions following each vaccination for 30 minutes. Subjects will return to the clinic on Days 3, 7 and 14 following each vaccination for clinical assessment.

Seventy-five (75) subjects will be progressively enrolled into one of 3 cohorts. The first 20 subjects (Cohort 1) will be randomized at a 3:1 ratio to receive either the 20 µg dose of AMA1-C1/Alhydrogel[®] + CPG 7909 or the 80 µg AMA1-C1/Alhydrogel[®] vaccine. After review of safety data at day 35 by the Safety Monitoring Committee (SMC) the study will proceed to Cohort 2. In Cohort 2, the next 20 subjects will be randomized 3:1 to receive either the 80 µg

dose of AMA1-C1/Alhydrogel[®] + CPG 7909 or the 80 µg AMA1-C1/Alhydrogel[®] vaccine, as outlined in the table below.

		Immunization Schedule		
Cohort	Total Volunteers	Day 0	Day 28	Day 56
1	20	A (15) or C (5)	A (15) or C (5)	A (15) or C (5)
2	20	B (15) or C (5)	B (15) or C (5)	B (15) or C (5)
3	35	B (15) or C (20)	B (15) or C (20)	B (15) or C (20)
TOTAL	75	A: 20 µg AMA1-C1/424 µg Alhydrogel [®] + 500 µg CPG 7909 B: 80 µg AMA1-C1/424 µg Alhydrogel [®] + 500 µg CPG 7909 C: 80 µg AMA1-C1/424 µg Alhydrogel [®]		

After evaluation of 35-day safety data in Cohort 2, and evaluation of all available safety data in Cohort 1, an additional 35 subjects (Cohort 3) will be randomized to receive the 80 µg AMA1-C1/Alhydrogel[®] either with or without CPG 7909 in a 3:4 ratio.

A Safety Monitoring Committee (SMC) will be asked to review cumulative safety data prior to dose escalation. Stopping rules for dose escalation are given in section 7.7.

A total of seventy five subjects will be enrolled. Forty five subjects will receive the AMA1-C1/Alhydrogel[®] + CPG 7909 vaccine (one of two dose concentrations), and 30 will receive the 80 µg AMA1-C1/Alhydrogel[®] vaccine.

3.3 MEASURES TO AVOID BIAS

Subjects within each cohort will be blinded as to study assignment.

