5.3 RANDOMIZATION

The eligible subjects assigned to each of the three cohorts will be asked to come to the clinic for their scheduled day 0 visit. After a history and physical exam is performed to ensure

that they are eligible for participation in the study, blood will be collected for the studies outlined in Section 5.21. Study participants will be assigned a unique study number.

Randomization to either the AMA1-C1/Alhydrogel[®] + CPG 7909 vaccine or 80 µg AMA1-C1/Alhydrogel[®] vaccine will be done online using the enrollment module of the Internet Data Entry System (IDES). The randomization codes will be included in the enrollment module for the trial. Each subject enrolled into the trial is assigned a treatment code after demographic and eligibility data have been entered into the system. The site will be provided with a code list to be kept in a secure place.

5.4 IMMUNIZATION PROCEDURE:

Subjects will receive three immunizations, on Days 0, 28, and 56. 0.50 mL of AMA1-C1/Alhydrogel[®] or 0.55 mL of AMA1-C1/Alhydrogel[®] + CPG 7909 will be delivered by IM in the deltoid muscle with a 22-gauge needle of appropriate length after preparation of the site with alcohol. Successive vaccinations will be given in alternating arms.

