7.3.1 Definition of Adverse Event

Adverse Event: ICH E6 Good Clinical Practice Guidelines defines an Adverse Event (AE) as any untoward medical occurrence in a patient or clinical investigation subject administered a pharmaceutical product regardless of its causal relationship to the study treatment. An AE can therefore be any unfavorable and unintended sign (including an abnormal laboratory finding), symptom, or disease temporally associated with the use of medicinal (investigational) product. The occurrence of an adverse event may come to the attention of study personnel during study visits and interviews or by a vaccine recipient presenting for medical care.

All adverse events must be graded for intensity and relationship to study product

Changes in the severity of an AE should be documented to allow an assessment of the duration of the event at each level of intensity to be performed. Adverse events characterized as intermittent require documentation of onset and duration of each episode.

Relationship to study products/vaccines: The investigator's assessment of an AE's relationship to study drug/vaccine is part of the documentation process, but it is not a factor in determining what is or is not reported in the study. If there is any doubt as to whether a clinical observation is an AE, the event should be reported. All adverse events must have their possible relationship to study vaccine assessed using the following terms: associated or not associated. In a clinical trial the study product must always be suspect. To help assess, the following guidelines are used.

- Associated – There is a known temporal relationship with study product administration and definite no other compelling etiology. Associated adverse events include those AEs judged to be definitely, probably, possibly, or unlikely related to vaccination.
- Not Associated -the AE is temporally independent of study product administration; and a compelling alternative etiology exists

Relationship of AEs to study product will be coded on a dual scale so that assignment of associated/not associated or definitely/probably/possibly/unlikely/not will both be captured and can be reported either way.

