7.4 REPORTING PROCEDURES

Adverse Events including local and systemic reactions not meeting the criteria for “serious adverse events” will be captured on the appropriate case report form. Information to be collected includes event description, date of onset, investigator assessment of severity, relationship to study product, date of resolution of the event, seriousness, and outcome. All adverse events occurring while on study will be documented appropriately regardless of relationship. All AEs will be followed to adequate resolution.

Any medical condition that is present at the time that the patient is screened will be considered as baseline and not reported as an AE. If the severity of any preexisting medical condition increases during the study period, then it will be recorded as an AE.

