9.2 Endpoints

9.2.1 Safety

The primary safety endpoint is the frequency of vaccine-associated AEs, as classified by severity through active and passive surveillance. Separate assessments of systemic and local reactions will be performed.

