13.2 DATA MANAGEMENT RESPONSIBILITIES

All source documents and laboratory reports must be reviewed by the clinical team and data entry staff, who will ensure that they are accurate and complete. Adverse Events must be graded, assessed for severity and causality and reviewed by the site Principal Investigator or designee. Data collection is the responsibility of the clinical trial staff at the site under the supervision of the site Principal Investigator. During the study, the Investigator must maintain complete and accurate documentation for the study.

The EMMES Corporation will serve as the Statistical and Data Coordinating Center for this study, and will be responsible for data management, quality review, analysis and reporting of the study data.

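### The protocol states blinding for subjects only, although the primary safety endpoint and several halting criteria rest on clinicians' examination, grading and causality calls

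*Protocol*

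**What the plan says.** **Who is blinded.** Section 3.3 (Measures to Avoid Bias) reads in full: "Subjects within each cohort will be blinded as to study assignment". Section 3.2 (Study Design) agrees: "The subjects will be blinded to which vaccine they are receiving". Neither mentions staff or laboratories.

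**What is counted.** Section 9.2.1: "The primary safety endpoint is the frequency of vaccine-associated AEs, as classified by severity through active and passive surveillance".

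**Who decides.** On causality, section 7.3.1 says "All adverse events must have their possible relationship to study vaccine assessed using the following terms: associated or not associated" and assigns the task: "The investigator's assessment of an AE's relationship to study drug/vaccine is part of the documentation process". Section 7.4 lists, among the data to be collected for each AE, "investigator assessment of severity, relationship to study product". Section 13.2 adds: "Adverse Events must be graded, assessed for severity and causality and reviewed by the site Principal Investigator or designee". The visit schedule in sections 5.5 to 5.19 has clinicians take an interim history and examine the subject, including the injection site at the early post-vaccination visits.

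**Who holds the codes.** Section 3.8 gives them to the study pharmacist, with a sealed backup held by the medical monitor at the site. Section 5.3 adds: "The site will be provided with a code list to be kept in a secure place".

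**What is injected.** Section 5.4 gives 0.50 mL without CPG 7909 and 0.55 mL with it.

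**The concern.** In each cohort subjects are randomised to vaccine with or without CPG 7909, so the trial yields concurrent AE rates for both. Those rates can be compared fairly only if the people who look for, grade and attribute events do so in the same way in both groups.

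Subject blinding does not secure that. An AE enters the primary endpoint only after a clinician has called it associated, and it is tabulated under the grade the clinician gave it. Section 1.4 warns staff of possible autoimmune effects and anti-dsDNA antibodies with CPG 7909. An assessor who knew the assignment could probe, grade or attribute differently in that group. The error could go either way: more events found because harm is expected, or fewer because the product is favoured.

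Two things are at stake: the credibility of the event rates, which section 9.1 says the study exists to estimate, and the halting decisions in section 7.7 that use the same judgements.

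**Working it through.** The point rests on no calculation. The only safety figure in the protocol is in section 9.4: with 15 subjects and an event rate of 0.1, the probability of seeing at least one event is 1 − 0.9^15 = 0.794, which agrees with the stated value of about 0.8. Blinding does not bear on it. The rest is a comparison of sections.

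**1. Is anyone other than the subject blinded?** Sections 3.2 and 3.3 name subjects. Sections 5 to 7, 9 and 13 describe examination, assays, AE assessment, analysis and data handling without saying that anyone performing them is blinded. The protocol calls the earlier Mali trial (1.2.2) and the Engerix-B and Fluarix trials (1.2.4) double-blind. The body of the protocol does not use that term for this trial.

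**2. Which safety data depend on a clinician's judgement?**

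- *Solicited reactions:* graded 0 to 3+ by the blinded subject on a diary card (7.3). Site reactions are sized with a standard device and entered in the diary (7.2). Erythema, swelling and fever have numeric cut-offs (17.2). Exposure is small.
- *Laboratory AEs:* most grades are numeric (17.3). Exposure is small for the grade. Causality is still a judgement.
- *Unsolicited AEs:* the subject can record these for six days after vaccination (7.3). After that they come through interim history and examination. Grading and attribution are the clinician's throughout. Exposure is greatest here.
- *Causality:* always the investigator's (7.3.1), and it decides whether the event enters the primary endpoint.

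**3. Do the same judgements drive decisions?** In section 7.7, criteria 1 and 2 require a serious AE or anaphylaxis to be called associated. Criterion 3 turns on whether a severe illness is explained by an unrelated diagnosis. Criteria 4 and 5 include graded physical findings and clinical AEs besides laboratory values.

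**4. Does the handling of codes and doses settle the matter?** Not fully.

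- Section 3.8 points to concealment. Section 5.3 then places a list at the site with no named holder. Under section 3.4 the kit carries the randomization code, so a person with both the kit and a list linking codes to vaccines could identify the group.
- The volumes differ by 0.55 − 0.50 = 0.05 mL, or 0.05/0.50 = 10% of the smaller volume. No masked syringe is described, and nothing keeps the person who injects from later assessing AEs.
- Sections 3.4.2.1 and 3.4.3 describe adding CPG 7909 to the vaccine vial. No matching step is described for the vaccine given alone, which comes in single-dose vials (3.4.1.1). Used vials go back to the pharmacy after administration (3.4.1.3), so they may have been in the clinic.

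**5. How exposed are the immunology assays?** ELISA and growth inhibition are absorbances converted by a standard curve or a formula (6.2.1, 6.2.2). Flow cytometry and ELISPOT leave more to the reader but serve an exploratory objective (2.2.4). Stored samples carry codes (6.3), though blinded reading is not stated. This is secondary to the safety point.

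**The case against.** The strongest reply is that silence is not unblinding. The pharmacist keeps the codes, the backup is sealed, kits carry a volunteer number and code, and the enrolment system issues a treatment code. All of this suggests that clinicians were meant not to know. This stands. A reader might infer that clinicians know the assignment, and the documents do not say so. What they lack is any statement that clinicians do not.

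A reader might also see a contradiction between sections 3.8 and 5.3. There is none that the text forces: the securely kept list could be the pharmacist's own. The holder is simply unnamed.

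The definition of *associated* is wide. It covers events judged unlikely to be related, while *not associated* calls for both temporal independence and a compelling other cause (7.3.1). Most events soon after vaccination would be *associated* in either group, which leaves less room for biased attribution. This stands. Some room remains because the five-level scale is also captured and may be reported, and because the width of the definition does nothing for severity grading or for how hard a clinician looks.

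Finally, the primary objective (2.1.1) is to assess the CPG 7909 vaccine, not to test it against the vaccine alone. Safety is descriptive (9.1, 9.3), and blinding subjects only can be a deliberate choice in an early trial. This also stands, so no test or error rate is affected. But a randomised group of 30 without CPG 7909 will be read as the comparator for AE rates. If single blinding is intended, section 3.3 should say so and deal with assessment.

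**Conclusion.** The point holds in this form: blinding is stated for subjects only, while the primary safety endpoint and several halting criteria depend on clinicians whose blinding is not stated, and the code list and unequal volumes leave ways for the assignment to become known. Blinding belongs in the protocol, which has its own section for it, so it cannot be left to a statistical analysis plan.

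Exposure lies mainly in unsolicited AEs, clinical examination and causality. It is smaller for diary reactions, numeric laboratory grades and plate-reader assays.

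No numerical size is claimed. A reader might want a figure for the false excess of AEs with CPG 7909, but the documents give no rate of differential grading or attribution. Any figure would rest on invented inputs, and a large gap in attribution between groups would fit poorly with the wide definition of *associated*. Nor do the documents support the inference that the antibody endpoint or its sample size is compromised.

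The conclusion assumes that no other trial document, such as the Manual of Procedures, already blinds the assessors. If one does, the protocol should say so. The change should be made, but the weakness does not invalidate the design.

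**What to change.** - **Section 3.3:** state that the clinicians who examine subjects and who grade and attribute AEs, and the laboratory readers, are blinded to vaccine group.
- **Section 5.3:** restrict the code list to the study pharmacist, with the medical monitor's sealed backup as the only other copy, in line with section 3.8.
- **Dosing:** have doses dispensed in masked syringes, or bar whoever handles an unmasked dose from AE assessment. If assessors cannot be blinded in general, say so and name a blinded assessor for severity and causality.
- **Laboratory samples:** label them with the study number only.
- **Section 9.3:** present AE rates by vaccine group regardless of attribution, beside the associated AEs. Most of this is already provided for. Section 7.4 records every AE whatever its relationship, and section 9.3 separates overall frequency from severity and relationship. However, section 9.3 stratifies by dose cohort, and each cohort contains subjects with and without CPG 7909, so *by vaccine group* should be explicit.

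The cost is protocol wording plus minor pharmacy and labelling work. The pharmacy's role is described only for the CPG 7909 mixture, so dispensing every dose masked may add a little work for the vaccine given alone. Opening the code in an emergency would go through the sealed copy that section 3.8 already provides.
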